7.5 INSTITUTIONAL BIOSAFETY COMMITTEE (IBC) REPORTING CRITERIA

7.5.1 *Serious Adverse Event Reports to IBC*

The Principal Investigator (or delegate) will notify IBC of any unexpected fatal or life-threatening experience associated with the use of rV-PSA(L155)-TRICOM and rF-PSA(L155)-TRICOM as soon as possible but in no event later than 7 calendar days of initial receipt of the information. Serious adverse events that are unexpected and associated with the use of the rV-PSA(L155)-TRICOM and rF-PSA(L155)-TRICOM, but are not fatal or life-threatening, must be reported to the NIH IBC as soon as possible, but not later than 15 calendar days after the investigator's initial receipt of the information. Adverse events may be reported by using FDA Form 3500a.

7.5.2 *Annual Reports to IBC*

Within 60 days after the one-year anniversary of the date on which the IBC approved the initial protocol, and after each subsequent anniversary until the trial is completed, the Principal Investigator (or delegate) shall submit the information described below. Alternatively, the IRB continuing review report can be sent to the IBC in lieu of a separate report. Please include the IBC protocol number on the report.

7.5.2.1 Clinical Trial Information

A brief summary of the status of the trial in progress or completed during the previous year. The summary is required to include the following information:

- the title and purpose of the trial
- clinical site
- the Principal Investigator
- clinical protocol identifiers;
- participant population (such as disease indication and general age group, e.g., adult or pediatric);
- the total number of participants planned for inclusion in the trial; the number entered into the trial to date whose participation in the trial was completed; and the number who dropped out of the trial with a brief description of the reasons
- the status of the trial, e.g., open to accrual of subjects, closed but data collection ongoing, or fully completed,
- if the trial has been completed, a brief description of any study results.

7.5.2.2 Progress Report and Data Analysis

Information obtained during the previous year's clinical and non-clinical investigations, including:

- a narrative or tabular summary showing the most frequent and most serious adverse experiences by body system
- a summary of all serious adverse events submitted during the past year
- a summary of serious adverse events that were expected or considered to have causes not associated with the use of the gene transfer product such as disease progression or concurrent medications
- if any deaths have occurred, the number of participants who died during participation in the investigation and causes of death
- a brief description of any information obtained that is pertinent to an understanding of the gene transfer product's actions, including, for example, information about dose-response, information from controlled trials, and information about bioavailability.

7.6 DATA AND SAFETY MONITORING PLAN

7.6.1 *Principal Investigator/Research Team*

The clinical research team will meet on a weekly basis when patients are being actively treated on the trial to discuss each patient. Decisions about dose level enrollment and dose escalation if applicable will be made based on the toxicity data from prior patients.

All data will be collected in a timely manner and reviewed by the principal investigator or a lead associate investigator. Adverse events will be reported as required above. Any safety concerns, new information that might affect either the ethical and or scientific conduct of the trial, or protocol deviations will be immediately reported to the IRB using iRIS and to the Sponsor).

The principal investigator will review adverse event and response data on each patient to ensure safety and data accuracy. The principal investigator will personally conduct or supervise the investigation and provide appropriate delegation of responsibilities to other members of the research staff.

7.6.2 *Sponsor Monitoring Plan*

As a sponsor for clinical trials, FDA regulations require the CCR to maintain a monitoring program. The CCR's program allows for confirmation of: study data, specifically data that could affect the interpretation of primary study endpoints; adherence to the protocol, regulations, and SOPs; and human subjects protection. This is done through independent verification of study data with source documentation focusing on:

- Informed consent process
- Eligibility confirmation
- Drug administration and accountability
- Adverse events monitoring
- Response assessment.

The monitoring program also extends to multi-site research when the CCR is the coordinating center.

This trial will be monitored by personnel employed by an NCI contractor. Monitors are qualified by training and experience to monitor the progress of clinical trials. Personnel monitoring this study will not be affiliated in any way with the trial conduct.

7.6.3 Safety Monitoring Committee (SMC)

This protocol will require oversight from the Safety Monitoring Committee (SMC). Initial review will occur as soon as possible after the annual NCI-IRB continuing review date. Subsequently, each protocol will be reviewed as close to annually as the quarterly meeting schedule permits or more frequently as may be required by the SMC. For initial and subsequent reviews, protocols will not be reviewed if there is no accrual within the review period. Written outcome letters will be generated in response to the monitoring activities and submitted to the Principal investigator and Clinical Director or Deputy Clinical Director, CCR, NCI.

8 STATISTICAL SECTION

The primary objective of this trial is to determine the effect of prostate cancer vaccine on CD4 and CD8 cell infiltrate staining.

The primary endpoints will be the changes from baseline to after surgery of the CD4 and CD8 cell infiltrates. The fold change from baseline to post surgery biopsy will be the primary endpoint for each measure. With two primary parameters to be measured with respect to a change at one time point, the sample size will be selected to allow each test to be performed using a 0.025 two-tailed significance level, in order to allow the overall set of two tests to be very conservatively performed as if at an overall 0.05 level using a Bonferroni adjustment. With 24 total patients with full measurements on both parameters at baseline and post-surgery, there would be 80% power to detect a change from baseline equal to 0.67 standard deviations of the change (0.67 effect size) using a two-tailed 0.025 level paired t-test. In practice, instead of requiring that each test achieve a 0.025 level in order to be declared significant, if appropriate to do so, a less overly stringent Hochberg adjustment may be performed. In addition, if the differences from baseline to post-surgery are not normally distributed (that is, if $p < 0.05$ by a Shapiro Wilks test) then a Wilcoxon signed rank test will be performed instead.

It is anticipated that 1-2 patients per month may enroll on this trial. Thus, it is expected that up to 2 years may be required to enroll 24 evaluable patients. In order to allow for a small number of inevaluable patients, the accrual ceiling for the trial will be set at 27 patients.

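### Section 8 names a fold change as the primary endpoint but writes its power and tests for differences; the analysis scale is not fixed, and testing an untransformed ratio would favour a false increase

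*Combined protocol and SAP*

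**What the plan says.** Section 8 describes the primary endpoint in two ways. It first says "The primary endpoints will be the changes from baseline to after surgery of the CD4 and CD8 cell infiltrates", which leaves the scale open. The next sentence narrows this: "The fold change from baseline to post surgery biopsy will be the primary endpoint for each measure".

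The operating rules that follow are on a different footing. The sample size allows "each test to be performed using a 0.025 two-tailed significance level", so that the pair of tests is "very conservatively performed as if at an overall 0.05 level using a Bonferroni adjustment". The power claim reads "there would be 80% power to detect a change from baseline equal to 0.67 standard deviations of the change", and the test is a paired t-test. The switch to the Wilcoxon signed rank test applies "if the differences from baseline to post-surgery are not normally distributed", judged by a Shapiro-Wilk p-value below 0.05.

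Other sections do not settle the matter. Section 5.1.1 expresses the measurement as stained cells per unit area, accepts slides from a single cancer-bearing core as the baseline, and leaves the choice of test open. Section 6.2.1.1 says only that densities before and after vaccine will be compared.

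**The concern.** A fold change and a difference are different quantities, with different null values and different sampling behaviour. The plan names one and gives rules for the other.

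The natural untransformed reading, post/pre tested against 1, is not neutral when nothing changes. A doubling scores +1 and a halving scores -0.5, so ratio minus 1 is right-skewed and its mean is above zero. The t-test inherits that upward pull. The signed rank test assumes symmetry about the null value, so switching to it reduces the problem without removing it. A baseline core with no stained cells makes the ratio undefined, and no rule covers that case.

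This is the trial's only comparison with a stated significance level, and the trial has a single arm. With the scale left open, it could be chosen after the staining results are known, and one available choice leans towards concluding that the vaccine raised the infiltrate.

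**Working it through.** **Inputs from Section 8:** 24 evaluable pairs, two-sided 0.025 per marker, effect size 0.67, paired t-test, Shapiro-Wilk threshold 0.05, Wilcoxon signed rank fallback, two markers at overall 0.05. **Assumed:** the spread *s* = SD of log(post/pre). The documents give none, so it runs from 0.2 to 1.0.

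**1. The plan's own figure.** Noncentral t with df = 23 and noncentrality 0.67 × √24 = 3.28 gives power 80.5% at two-sided 0.025. An effect of 0.666 gives exactly 80%. The stated power is reproduced.

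**2. Mean ratio with no true change.** If log(post/pre) is normal with mean 0 and SD *s*, the mean ratio is exp(*s*²/2). It is 1.02 at *s* = 0.2, exp(0.125) = 1.13 at *s* = 0.5, and exp(0.5) = 1.65 at *s* = 1.0. A t-test of the mean ratio against 1 is therefore testing a null that is false even when the vaccine does nothing.

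**3. Rejection rates with no true change.** Simulation of 40,000 trials per setting, n = 24, with pre and post values independent lognormals of the same distribution. All tests are two-sided at 0.025. Switch means t-test or Wilcoxon according to Shapiro-Wilk.

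| *s* | Ratio vs 1, t-test alone | Ratio vs 1, Wilcoxon alone | Ratio vs 1, switch judged on ratios | Ratio vs 1, switch judged on differences | Difference, switch | Log ratio, switch |
|---|---|---|---|---|---|---|
| 0.2 | 0.031 | 0.026 | 0.032 | 0.032 | 0.026 | 0.026 |
| 0.3 | 0.038 | 0.030 | 0.038 | 0.039 | 0.026 | 0.026 |
| 0.5 | 0.057 | 0.036 | 0.049 | 0.056 | 0.025 | 0.025 |
| 0.7 | 0.084 | 0.050 | 0.060 | 0.080 | 0.025 | 0.026 |
| 1.0 | 0.120 | 0.068 | 0.072 | 0.108 | 0.024 | 0.025 |

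Simulation error is about 0.001 at 0.025 and 0.002 at 0.12. Shorter runs of the switch judged on ratios gave 0.031 to 0.034 at *s* = 0.2 and 0.076 to 0.078 at *s* = 1.0, hence the rounded range 0.03 to 0.08. A shorter run with pre and post values correlated at 0.5 gave similar ratio results at the same *s*.

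**4. Direction.** At *s* = 0.5, 0.054 of the 0.057 t-test rejections on ratios are increases. A balanced test at 0.025 would put 0.0125 on each side.

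**5. Two markers.** With independent markers the chance of at least one false positive is 1 − (1 − p)². Using the switch judged on ratios:
- *s* = 0.2: 1 − (1 − 0.0317)² = 0.062
- *s* = 0.5: 1 − (1 − 0.0486)² = 0.095
- *s* = 1.0: 1 − (1 − 0.0717)² = 0.138

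With the two markers correlated at 0.5 the range is 0.059 to 0.137. The target is 0.05.

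**6. Log scale.** The last column holds at 0.025 to 0.026 throughout. Reading 0.67 as SDs of the log ratio leaves step 1 unchanged: 80.5% at 24 pairs.

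**The case against.** The strongest reply is that the plan never proposes testing ratios against 1. Its rules describe ordinary paired data: a paired t-test, an effect in SDs of the change, normality judged on differences, and a matched-pair signed rank test in Section 5.1.1. Followed literally, they hold the level at 0.024 to 0.026. Fold change may have been meant as a log ratio, or only as a descriptive summary. The spread is unknown, and at *s* = 0.2 to 0.3 the inflation is modest even on raw ratios. This is also a small Phase II trial meant to inform later work.

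Most of this stands. A reader might infer that the plan commits to a raw-ratio test and that its overall 0.05 level therefore fails. The documents do not support that: they do not say raw, they do not state a null of 1, and of the three scales checked, differences and log ratios keep the level.

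The reply does not remove the mismatch. Section 8 calls the fold change the primary endpoint, not a summary, and no sentence links it to the differences that are tested. The log reading would resolve this, but it is nowhere stated.

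Two related points carry little weight. The reference to a biopsy after surgery is a slip, since Sections 1.2.4, 5.1.1 and 6.2.1.1 make clear that the later sample is the prostatectomy specimen. Zero baseline densities are a real gap on any ratio scale, but the documents give no indication of how often they will occur.

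**Conclusion.** The point holds as an unresolved choice of analysis scale. Section 8 names one quantity as primary and gives power, test and normality rules for another. Testing differences keeps the error near 0.025 but leaves the named endpoint untested.

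Testing the untransformed ratio against 1 raises the per-marker error to about 0.03 to 0.08 when the switch is judged on the ratios. It reaches about 0.11 at the widest spread if the switch is judged on differences, and about 0.12 for the t-test alone. The two-marker error, with the switch judged on ratios, is about 0.06 to 0.14 against 0.05. The excess is almost all false increases.

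These sizes are conditional on that reading, on lognormal ratios and on an assumed log-SD of 0.2 to 1.0. They are not a property of the plan as written. The sample size of 24 and the 80% power are not in error.

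**What to change.** In Section 8:

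- Define the primary endpoint for each marker as log(prostatectomy density / baseline biopsy density), tested against 0 and reported as a geometric mean fold change with its confidence interval.
- Apply the existing Shapiro-Wilk/Wilcoxon rule to that same quantity. Keeping or dropping the normality gate is optional, since the gated rule also holds the level on this scale.
- Fix one offset for zero densities before any staining results are seen.
- State the 0.67 effect size in SDs of the log ratio.
- As a clerical correction, name the prostatectomy specimen as the later sample.

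The cost is a few sentences, with no added patients, samples or assays and no change to the 24 evaluable pairs. The one drawback is that the zero offset is somewhat arbitrary and would not be needed for absolute differences, which is why it must be set in advance.

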9 COLLABORATIVE AGREEMENTS

9.1 AGREEMENT TYPE

The clinical grade vaccines used in this protocol were prepared by Bavarian Nordic, Inc. as part of an ongoing CRADA with the LTIB, CCR, NCI.

Sharing of samples/data will be facilitated through approved Material Transfer Agreements (MTA).

10 HUMAN SUBJECTS PROTECTIONS

10.1 RATIONALE FOR SUBJECT SELECTION

10.1.1 Selection Based on Gender, Ethnicity, and Race

Subjects from all racial/ethnic groups are eligible for this study if they meet the eligibility criteria. To date, there is no information that suggests that differences in drug metabolism or disease response would be expected in one group compared with another. Efforts will be made to extend accrual to a representative population, but in this preliminary study, a balance must be struck between patient safety considerations and limitations on the number of individuals exposed to potentially toxic and/or ineffective treatments on one hand and the need to explore gender and ethnic aspects of clinical research on the other hand. If differences in outcome that correlate with ethnic identity are noted, accrual may be expanded or a follow-up study may be written to investigate those differences more fully.

10.1.2 Strategies/Procedures for Recruitment

Our patient accrual for this protocol would be facilitated by the Clinical Center Support Center (CCSC), developed to increase the accrual to clinical studies via community outreach as well as recruitment letters to referring physicians.

This protocol will be available through the physicians' data query (PDQ) database.

10.1.3 Justification for Exclusions

Due to impaired cellular immunity, HIV patients are at an increased risk of serious side effects from vaccinations with infectious agents and are excluded.

10.2 PARTICIPATION OF CHILDREN

Individuals under the age of 18 will not be eligible for participation in this study based on the fact that patients under 18 are unlikely to have this disease and unknown toxicities in pediatric patients.

10.3 PARTICIPATION OF SUBJECTS UNABLE TO GIVE CONSENT

Adults unable to give consent are excluded from enrolling in the protocol. However re-consent may be necessary and there is a possibility, though unlikely, that subjects could become decisionally impaired. For this reason and because there is a prospect of direct benefit from research participation (section 10.5), all subjects \geq age 18 will be offered the opportunity to fill in their wishes for research and care, and assign a substitute decision maker on the "NIH Advance Directive for Health Care and Medical Research Participation" form so that another person can make decisions about their medical care in the event that they become incapacitated or cognitively impaired during the course of the study. Note: The PI or AI will contact the NIH Ability to Consent Assessment Team for evaluation. For those subjects that become incapacitated and do not have pre-determined substitute decision maker, the procedures described in MEC Policy 87-4 for appointing a surrogate decision maker for adult subjects who are (a) decisionally impaired, and (b) who do not have a legal guardian or durable power of attorney, will be followed.

10.4 EVALUATION OF BENEFITS AND RISKS/DISCOMFORTS

For patients with localized prostate cancer, the gold standard of care can include active surveillance, radical prostatectomy, or radiation therapy. No current optimal neoadjuvant

treatment protocol is as yet established even in high risk patients with a significant risk of biochemical recurrence. PSA vaccines using pox vectors have been studied as neoadjuvant therapy in Phase II trials in patients undergoing radiation treatment with good immune response. Potential risks include the possible occurrence of any of a range of side effects listed in section 11.

10.4.1 Alternative Approaches or Treatments

Patients will be consented verbally and in writing regarding the risks and benefits of this trial, the treatment requirements, and alternative approaches to entering on this trial.

10.4.2 Procedure for Protecting Against or Minimizing any Potential Risks

All care will be taken to minimize side effects, but they can be unpredictable in nature and severity. This study may involve risks to patients, which are currently unforeseeable. All patients will have blood tests, examinations and scans as described in the monitoring schedule (section 3.5). Patients will also be required to have a local physician to provide long-term care and to monitor for complications. If patients suffer any physical injury as a result of the participation in this study, immediate medical treatment is available at the Clinical Center, National Cancer Institute, Bethesda, Maryland. Although no compensation is available, any injury will be evaluated and treated in keeping with the benefits or care to which patients are entitled under applicable regulations.

10.4.3 Provisions for Monitoring Data Collection to Ensure Safety of Subjects

As information is gathered from this trial, clinical results will be shared with patients. Laboratory and clinical data will be frequently gathered and any new significant finding(s) found during the course of the research, which may affect a patient's willingness to participate further, will be explained.

Confidentiality of information concerning participants will be maintained, including in all publications and presentations resulting from this study. Names of participants or material identifying participants will not be released without permission, except as such release is required by law. Records at the National Cancer Institute are maintained according to current legal requirements, and are made available for review, as required by the Food and Drug Administration or other authorized users, only under the guidelines established by the Federal Privacy Act.

10.4.4 Risk-Benefit Ratio in Target Population

Among normal patients who have received prior vaccination, there is an overall **0.0108%** complication rate (see table below).

The overall risk in vaccinia naïve patients is slightly higher at 0.1253%

Complication Rates—Vaccinia (cases per million vaccines)*

Complication	Rate
Inadvertent inn.	42
E. multiforme	10
Generalized vacc	9
E. vaccinatum	3
V. necrosum	3

Encephalitis	2
Other**	39
Total	<hr/> 108

*Adapted from Lane et al., J. Infect. Dis. 1970;122:303-309.

**Ind. bacterial superinfections and lesions uncomfortable enough to result in physician contact. Unusual complications ind. fetal vaccinia, melanoma at vaccine scar, and monoarticular arthritis.

However, this risk is reduced by a factor of 10 if the patient has previously received vaccinia virus, either through the smallpox vaccination program or through other recombinant virus clinical trials (MMWR, June 22, 2001/50(RR10);1-25). This reduces the overall risk of vaccinia immunization to 0.0108%. It should be noted that the complication rates predominantly include inadvertent autoinoculation, i.e., autologous transmitting of virus from inoculation site to face and hands. When the complication rates are stratified and only severe cases examined, the adjusted risk is 0.00005%.

There is an expected accrual of 27 patients for this protocol. The actual expected risk of vaccine complications (including dissemination) on a per patient basis remains 0.0108%.

In the rare cases of vaccinia immunization complications of any type (with the exception of vaccinia keratitis), the Center for Disease Control maintains a supply of VIG (see below). Contact Information: Emergency: [contact]; Routine: [contact]; [contact].

Vaccinia immunoglobulin:

- Must be available to give vaccinia safely
- Is available from CDC Drug Service and U.S. Army
- Dose: 0.6 ml/kg IM (can be given at multiple sites/Divided doses over 24–36 hours)
- Humanized monoclonal antibodies
 - promising; not yet available
 - against neutralizing epitopes conserved between variola and vaccinia

As to the risk-benefit ratio of vaccinia virus dissemination in the target population, the overall risk has been assessed at 0.0108%. The benefit cannot be estimated, as this is an experimental therapy. Noting the patient population (non-immunocompromised, metastatic prostate cancer (failed primary therapy)), however, it can be inferred that the ratio of risk of complications from metastatic prostate cancer to the risk of vaccinia virus dissemination in the target population would be large.

